9.7. Data analysis

[figure not shown]
Detailed methodology for summary and statistical analyses of data collected in this study will be documented in a separate statistical analysis plan (SAP), which will be dated, filed and maintained by the sponsor. The SAP may modify the plans outlined in the protocol; any major modifications of primary endpoint definitions or their analyses would be reflected in a protocol amendment.

Analyses will be performed by pH Associates using Stata (StataCorp LLC) and R statistical software (version 3.4.1 or later). Data from all participating centres will be pooled for analysis.

Descriptive statistics (number, percentages, means, standard deviations, medians, quartiles, minimum, maximum, number of missing and non-missing values), as appropriate to the data collected, will be used to describe baseline demographic and clinical characteristics for the overall study. Treatment patterns, treatment outcomes and TRAEs will also be reported using descriptive characteristics. Frequency and percentages will be used to describe categorical variables. All percentages will be reported to the nearest whole number; therefore, in reporting study results in tables, figures and associated text, percentages may not add up to 100% due to rounding. Means, standard deviations, medians, quartiles, minimum, and maximum, will be used to describe continuous variables. Patients who are still alive and have not progressed at the last visit date without clinical evidence of progression will be censored. Kaplan-Meier plots will be used to describe data related to OS, RFS and time to CR/CRi. A summary table of the number of events and censored patients at each monthly interval will also be included.

The CR/CRI rate will be estimated as the proportion of patients who achieve CR/CRI divided by the total number of patients completing treatment with InO (defined as patients with a recorded date of discontinuation of InO). The MRD negativity rate will be defined as the proportion of patients in whom MRD-negative status is observed, among patients in whom MRD negativity status has been assessed, at any time until the end of treatment with InO (defined as the date of recorded discontinuation of InO). Patients who have not completed treatment with InO will not be included in CR/CRI rate and MRD negativity rate estimations. Date of 95% confidence intervals (CI) for CR/CRI rates and MRD negativity rates will be estimated using the Clopper-Pearson method. OR, RFS and NRM will be implemented according to their definition.

CCI

Where dates are ambiguous because of missing day and/or months, standard imputation will be applied: where day is missing the 15th of the month will be assumed; where both day and month are missing the 1st July will be assumed. Where data other than dates are missing from the original medical record, the affected analyses will be conducted using only the results of those patients with data available and the number included in each analysis will be stated. The percentage of data missing will be reported for each study variable. Note that the multivariate model will only include those patients with non-missing values for all covariates.

9.8. Quality control

All data collectors will be provided with Data Collection Guidelines to facilitate consistent completion of the eCRF and will receive training in the requirements of the study protocol and correct completion of the eCRF prior to commencement of data collection.

The accuracy and quality of data collection will be monitored by reference to source data (source data verification [SDV]).

SDV will be performed on the complete dataset of a random sample of at least 10% of patients from each centre. Any issues identified by pH Associates relating to quality, accuracy or consistency of data collection will be discussed with the data collector concerned

and further training provided by pH Associates if required. If any subsequent issues are identified related to quality, accuracy or consistency of data collection, a random check of a further 10% of data collected by that data collector will be undertaken. Should any further issues be identified, 100% SDV will be undertaken at the centre. It is the Investigator's responsibility at each centre to ensure the accuracy of the data entered into the CRFs.

A 'back-to-back' SDV monitoring methodology will be performed with a member of the direct care team. This will involve the direct care team member at the centre reciting data from the patient notes to the pH Associates study monitor so that they can verify the data in the eCRF without the need to look directly at the identifiable source records. All people performing SDV will be trained by pH Associates.

All clinical data submitted will be checked for eligibility, completeness and accuracy and queries will be raised by the pH Associates data management team using agreed manual and programmed validation checks. Study centres will be required to co-operate with the data management team in the resolution of these queries.

Analysis of the primary endpoint will be independently reviewed by a member of the Data Analysis team at pH Associates who was not involved in the analysis of the final study data. No additional analysis checks will be carried out.

9.9. Limitations of the research methods

- Several sources of selection bias may be introduced in the study:
 - Patients treated as part of the CUP may differ from patients treated via private purchase and patients treated via NHS commissioning.
 - Patients were recruited from larger centres enrolled in the CUP, which may differ from smaller centres in terms of demographic and clinical characteristics, and therefore may not be representative of all real-world patients treated with InO.
- Patients may be lost to follow-up due to the occurrence of AEs, lack of efficacy or other reasons. The use of Kaplan-Meier curves to obtain estimates of median OS, RFS and time to CR/Cri takes into account patients' attrition.
- The interpretation of data collected retrospectively will be dependent on the completeness and quality of the medical records and the reliability of the abstraction of data from the medical records. However, SDV will be employed to identify and correct abstraction errors.

- This is a descriptive study and no analyses to control for confounding will be carried out; therefore, no definitive causal relationships between InO and study endpoints can be made.
- The overall sample size of the study is relatively small, and therefore CR/CRI rates and MRD negativity rates may be estimated with relative imprecision, and 95% CIs may be relatively wide. In addition, the small sample size may not allow the conduct of univariate and multivariate Cox modelling to estimate the risk of VOD/SOS in patients with follow-up HSCT.

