9.2.1. Inclusion criteria

The source population for this study is adult patients treated with InO at the selected sites and who accessed InO *via* NHS commissioning, *via* the CUP or *via* private purchase between June 2016 and February 2019. The NICE recommendation is as an option for treating relapsed or refractory CD22- positive B-cell precursor ALL in adults; and patients with relapsed or refractory Philadelphia chromosome positive disease should have had at least 1 tyrosine kinase inhibitor⁹ (see **Annex 1** for NICE eligibility criteria). The eligibility criteria for inclusion in the CUP are provided in Annex 1.

Patients will be eligible for inclusion in the present study if they fulfill all of the following criteria:

Inclusion criteria

- Patients with relapsed/refractory ALL.
- Patients who initiated InO between 1st of June 2016 and date of data collection.
- Patients who accessed InO treatment *via* NHS commissioning, via the CUP, or via private purchase.
- Patient aged ≥ 18 years old at initiation of InO treatment

Exclusion criteria

- Patients initiated on treatment with InO at a different hospital than the ones selected in this study.
- Patients with <3 months of follow-up since index date, unless death occurs <3 months from index date.

Eligible patients will be selected by chronological order and with a priority given to patients treated *via* NHS commissioning, if possible.

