Complete Remission (CR): defined as documented in medical records or (if unavailable in the records) as < 5% blasts in the bone marrow and the absence of peripheral blood leukaemic blasts, full recovery of peripheral blood counts (platelets $\geq 100 \times 10^9/L$ and absolute neutrophil counts (ANC) $\geq 1 \times 10^9/L$) and resolution of any extramedullary disease.

Complete Remission with incomplete haematological recovery (CRi): defined as documented in medical records or (if unavailable in the records) as < 5% blasts in the bone marrow and the absence of peripheral blood leukaemic blasts, incomplete recovery of peripheral blood counts (platelets $< 100 \times 10^9/L$ and ANC $< 1 \times 10^9/L$) and resolution of any extramedullary disease.

Minimal Residual Disease (MRD) negativity: patients with ALL may be in remission (CR/CRi) although they may still harbour a large number of undetected malignant cells (MRD), and as such may be more susceptible to relapse. MRD describes diseases that can be diagnosed by methodology other than conventional morphology, and includes molecular methods like PCR, or immunophenotyping by flow-cytometry¹⁸. MRD negativity will be defined as documented in medical records or (if unavailable in the records) as leukaemic cells comprising $< 1 \times 10^{-4}$ ($< 0.01\%$) of bone marrow nucleated cells.

CR/CRi Rate: proportion of patients who achieve CR/CRi at the end of treatment with InO.

MRD negativity Rate: the proportion of patients in whom MRD-negative status is observed at the end of treatment with InO (2-3 cycles of 3-4 weeks each in patients proceeding to follow-up HSCT, and up to 6 cycles of 3-4 weeks each otherwise).

Overall Survival (OS): time from index date to death. Patients will be censored at the end of the post-index observation period.

Relapse Free survival (RFS): time from index date to earliest date of the following events: death, progressive disease (including objective progression, relapse from CR/CRi, treatment discontinuation due to global deterioration of health status), and start of new induction therapy or post-therapy HSCT without achieving CR/CRi; as documented in medical records (if unavailable, infer using definitions above). Patients will be censored at the end of the post-index observation period.

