For the estimation of endpoints, the following definitions will be implemented. The index date will be defined as the date of initiation of the first cycle of InO. CR/CRi rate will be defined as the number of patients who achieve CR/CRi divided by the total number of patients completing treatment with InO (defined as patients with a recorded date of discontinuation of InO). The MRD negativity rate will be defined as the proportion of patients in whom MRD-negative status is observed, among patients in whom MRD negativity status has been assessed, at any time until the end of treatment with InO (defined as the date of recorded discontinuation of InO). OS will be defined as the time from index date to death,

RFS will be defined as the time from index date to the earliest date of the following events: death, progressive disease (including objective progression, relapse from CR/CRi, treatment discontinuation due to global deterioration of health status), and start of new induction therapy or post-therapy HSCT without achieving CR/CRi. NRM will be defined as the time from date of follow-up HSCT until death without disease progression or relapse. Deaths from any cause without prior progression are events. Events related to the disease such as relapse or progression are competing events. Patients who are lost to follow-up will be censored at the last known visit date. Patients who are still alive at the study cut-off date (31st December 2020) or the last visit date available will be censored (at whichever occurred first).

Figure 1. Study design and observation periods

The baseline period is 6 months prior to the index date. All other time periods shown are variable for each patient.

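### Protocol 9.9 treats Kaplan-Meier as handling loss due to adverse events or lack of efficacy; it does so only if lost patients keep the same prognosis, so OS, and less so RFS, may be overstated with no planned check

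*Protocol*

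**What the plan says.** Protocol 9.9 (Limitations) makes two statements in sequence. The first gives the reasons for attrition: "Patients may be lost to follow-up due to the occurrence of AEs, lack of efficacy or other reasons". The second gives the remedy: "The use of Kaplan-Meier curves to obtain estimates of median OS, RFS and time to CR/Cri takes into account" the attrition of patients.

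SAP 3.1.1 sets the censoring rules. For losses: "Patients who are lost to follow-up will be censored at the last known visit date". For survivors: "Patients who are still alive at the study cut-off date (31st December 2020) or the last visit date available will be censored", at whichever date comes first. Both groups enter the analysis as the same kind of censored observation.

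The planned description of censoring is a count. Protocol 9.7 says: "A summary table of the number of events and censored patients at each monthly interval will also be included". SAP 10.1.5, 10.2.5 and 10.2.6 repeat this. None of them splits the count by reason.

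Three other provisions bear on the point:
- The RFS definition (Protocol Annex 2, SAP 3.1.1) counts as events death, progression, relapse, "treatment discontinuation due to global deterioration of health status", and new induction therapy or HSCT without CR/CRi.
- Protocol 9.2.1 excludes "Patients with <3 months of follow-up since index date, unless death occurs <3 months from index date".
- The Annex 2 dataset records final patient status, including a not-known category for loss to follow-up, with the date of the last hospital visit.

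**The concern.** Kaplan-Meier removes a censored patient from the risk set and lets those who remain stand in for that patient. This is valid when censoring is unrelated to prognosis. Two of the three reasons named in 9.9, toxicity and treatment failure, are plausibly related to it. The section thus describes a likely breach of the assumption and offers as the remedy the method that depends on it.

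If patients who are deteriorating stop attending the study site, their deaths are missed and the survival curve sits too high. OS and RFS carry much of the study's effectiveness description. A report that repeats 9.9 would tell readers that the problem had been dealt with. The confidence interval would not warn them, because it reflects sampling error only.

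**Working it through.** The documents give no loss rate or bias figure, so there is nothing of the plan's own to reproduce. The calculations below are illustrations.

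**Inputs from the documents.** Median OS 7.7 months and median progression-free survival 5.0 months on InO in the phase III trial (Protocol 7); about 25 patients (Protocol 9.5).

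**Assumptions.** Exponential survival, the share lost, and how strongly loss is tied to death.

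**1. Strong dependence.** True OS is exponential with median 7.7 months, so true 12-month OS is exp(-ln 2 × 12/7.7) = 34.0%. Administrative censoring is uniform over 6-36 months. A fraction f is due to be lost one month before death (halfway to death if death comes within two months). Large simulations, which agree with one another to about 0.1 month, give:

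| f | Kaplan-Meier median, months (true 7.7) | Kaplan-Meier 12-month OS (true 34.0%) |
|---|---|---|
| 5% | 8.0-8.1 | not tabulated |
| 10% | 8.5 | 37.5% |
| 20% | 9.4-9.5 | 41.6% |
| 30% | 10.7-10.8 | 46.2% |

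**2. Milder dependence.** Let the death hazard be λ before loss and kλ after it, with loss hazard g. If p is the share lost before the event, g = λp/(1-p). Kaplan-Meier estimates exp(-λt), while true survival is

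S(t) = exp(-(λ+g)t) + g[exp(-kλt) - exp(-(λ+g)t)]/(λ+g-kλ).

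Here the Kaplan-Meier median is held at 7.7 months, so λ = ln 2/7.7 = 0.0900, and the true median is solved for. Example with p = 30%, k = 2: g = 0.0900 × 0.3/0.7 = 0.0386. At t = 6.98, S = 0.4075 + (-0.750)(0.2846 - 0.4075) = 0.50. The true median is 6.98, an overstatement of 0.72 months.

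| Lost | True median, k = 0.5 | k = 1 | k = 2 | k = 3 | k = 5 |
|---|---|---|---|---|---|
| 5% | 7.78 | 7.70 | 7.59 | 7.52 | 7.44 |
| 10% | 7.87 | 7.70 | 7.48 | 7.34 | 7.19 |
| 20% | 8.09 | 7.70 | 7.24 | 6.97 | 6.68 |
| 30% | 8.37 | 7.70 | 6.98 | 6.58 | 6.16 |

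For k = 2 to 5, the overstatement is 0.1-0.3 months at 5% lost and 0.7-1.5 months at 30%. At k = 1 there is none. At k = 0.5 Kaplan-Meier understates OS.

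**3. RFS.** The same formula with a Kaplan-Meier median of 5.0 months gives a true median of 4.8-4.9 at 5% lost and 4.0-4.5 at 30% (k = 2 to 5). This supposes that none of the losses is recorded as an RFS event.

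**4. The exclusion of living patients with under 3 months of follow-up.** It removes early censored patients and keeps early deaths, so it pulls the estimate down. Under milder dependence, with entry assumed uniform over 55 months, it moves the Kaplan-Meier median from 7.7 to about 7.6 with no loss and to about 7.4-7.5 at 30% lost. At 5% lost with k = 2 it nearly cancels the bias (7.60 against a true 7.59). Under strong dependence it barely helps: at 10, 20 and 30% lost the medians are still about 8.4, 9.4 and 10.6.

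**5. Counting lost patients as events at last contact, strong dependence.** Without the exclusion, the medians at 10, 20 and 30% are about 7.6, 7.5 and 7.4. With it, they are about 7.9, 8.2 and 8.4-8.5, all above the true 7.7, because the earliest losses never enter the dataset.

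**6. Sampling error.** With 25 patients and a true median of 7.7, the Kaplan-Meier median has a 95% sampling range of about 4 to 13-15 months.

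**The case against.** The strongest reply is that the bias is hypothetical and modest for this study. Protocol 9.9 says only that patients may be lost, and it includes other reasons, which could be neutral or favourable. Much of the loss from lack of efficacy is already an RFS event if the chart records it. The early-follow-up exclusion pulls the other way. Monthly censoring counts show how much censoring occurs and when. The study is descriptive, OS and RFS are secondary, and with about 25 patients sampling error exceeds the bias in most of these scenarios.

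Most of this stands, and it limits the point. A reader might infer from 9.9 that OS and RFS are overstated as a matter of fact. The documents do not support that: they give no loss rate, the direction depends on who is lost, and RFS is less exposed than OS. A reader might also infer that the main analysis and a lost-as-event analysis would enclose the true value. Under this plan's exclusion rule they need not (step 5), and if healthier patients are the ones lost, the truth can lie above both.

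What the reply does not do is make the sentence in 9.9 correct. Unsplit monthly counts show neither the reason for censoring nor its effect. Wide intervals do not excuse an unexamined systematic error, and with 25 patients five losses are already 20%.

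**Conclusion.** The point holds in conditional form. Kaplan-Meier does not correct for outcome-related loss. OS, and to a lesser degree RFS, may be overstated, and neither document states the assumption or plans an analysis to examine it.

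The size is unknown until losses are counted. With a median OS near 7.7 months, it runs from nothing (loss unrelated to prognosis), through roughly 0.1-1.5 months (5-30% lost, later hazard two to five times higher), to about 3 months in the strong case with 30% lost. Loss shares, hazard ratios, timing of loss, exponential survival and the censoring patterns are all assumed. The method error is certain; the direction and size of any bias are not.

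**What to change.** 1. In Protocol 9.9, replace the Kaplan-Meier sentence with a statement that the method assumes loss unrelated to prognosis and that this may not hold here. If the protocol is not being amended, put the statement in the SAP and in the report's limitations.
2. In SAP 10.1.5, 10.2.5 and 10.2.6, split censored patients into lost and administratively censored and report both counts. Use the lost-to-follow-up status already in the Annex 2 dataset. Do not infer loss from a date rule such as no contact in the last 3 months: follow-up ends at the latest visit, so living patients with infrequent visits would be labelled lost.
3. Add one sensitivity Kaplan-Meier analysis each for OS and RFS that counts lost patients as events at last contact. Show its median and 12-month estimate beside the main result, labelled as a pessimistic scenario and not as a bound on the truth.
4. Beside it, report how many living patients were excluded for under 3 months of follow-up.

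The cost is one sentence, one flag from a field already planned, one extra run per endpoint, and a count taken at screening. The main analysis is unchanged. Protocol 9.7 allows the SAP to modify the planned analyses, and these endpoints are secondary. The downside for the sponsor is that a less favourable estimate appears in the report.

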9.10. Other aspects

Not applicable.

10. PROTECTION OF HUMAN SUBJECTS

10.1. Patient Information

All parties will comply with all applicable laws, including laws regarding the implementation of organizational and technical measures to ensure protection of patient personal data. Such measures will include omitting patient names or other directly identifiable data in any reports, publications, or other disclosures, except where required by applicable laws.

The personal data will be stored at the study site in encrypted electronic form and will be password protected or secured in a locked room to ensure that only authorized study staff has access. The study site will implement appropriate technical and organizational measures to ensure that the personal data can be recovered in the event of disaster. In the event of a potential personal data breach, the study site shall be responsible for determining whether a personal data breach has in fact occurred and, if so, providing breach notifications as required by law.

To protect the rights and freedoms of natural persons with regard to the processing of personal data, when study data are compiled for transfer to Pfizer and other authorized parties, patient names will be removed and will be replaced by a single, specific, numerical code, based on a numbering system defined by Pfizer. All other identifiable data transferred to Pfizer or other authorized parties will be identified by this single, patient-specific code. The investigator site will maintain a confidential list of patients who participated in the study, linking each patient's numerical code to his or her actual identity. In case of data transfer, Pfizer will maintain high standards of confidentiality and protection of patients' personal data consistent with the Clinical Study Agreement and applicable privacy laws.

10.2. Patient Consent

The direct care team for each patient will be involved in extracting data and will produce pseudo-anonymized records from identifiable patient's records which will be collected for the purpose of this study, at all time preserving confidentiality. As this study involves pseudo- anonymized structured or unstructured data, which according to applicable legal requirements do not contain data subject to privacy laws, obtaining informed consent from patients by Pfizer is not required.

10.3. Patient Withdrawal

Not applicable

10.4. Institutional Review Board (IRB)/Independent Ethics Committee (IEC)

This study does not require IRB/IEC approval and an IRB/IEC review is not required as all confidential data will only be accessed via the direct care team. This protocol will be submitted for approval to the Health Research Authority.

